This trial will investigate the dose of OPC-61815 that achieves tolvaptan exposure similar to tolvaptan 15-mg tablet in patients with heart failure. At the same time, plasma drug concentration data will be collected for evaluation of the pharmacokinetics following multiple OPC-61815 administration in patients with heart failure. For Day 1 of the treatment period, a blood will be collected predose, at the simulated t_{max} of OPC-61815 (1 hour after the start of administration), 3 time points around the t_{max} of tolvaptan (1, 1.5, and 2 hours after the start of administration), 3 time points in the estimated elimination phase of OPC-61815 (2, 4, and 6 hours after the start of administration), 3 time points in the estimated elimination phase of tolvaptan (6, 12, and 24 hours after the start of administration). These have been selected to calculate relevant pharmacokinetic parameters of OPC-61815 and tolvaptan based on the simulation of 1-hour intravenous administration using a population pharmacokinetic model based on data from 3 trials (the single intravenous dose trial of OPC-61815 in healthy adults [263-08-001], repeated intravenous dose trial of OPC-61815 in healthy adults [263-09-001], and trial investigating the rate of intravenous OPC-61815 administration in healthy adults [263-10-005]) and considering feasibility referring clinical pharmacology trial in Japanese patients with heart failure (156-06-004). One sampling time point (24 hours after the start of administration) for each of Day 2, Day 3, Day 4, and Day 5 of the treatment period is selected to confirm steady-state has been reached. A total of 12 blood sampling time points will be selected.

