3.4 Handling of Time Points

CRF Visit values at each time point (run-in period, treatment period, and follow-up) will be used in summaries (but values at the time of discontinuation will not be used in summaries). Unscheduled Visit values will not be used.

Baseline and final administration time point for each variable are defined as follows.

Variable	Baseline ^a	Final Administration Time Point
Body weight	Before IMP administration on Day 1	Day after final IMP administration
Congestive symptoms	Run-in period (final measurement)	Day after final IMP administration
Pulmonary congestion, cardiothoracic ratio	Run-in period	Day after final IMP administration
NYHA classification	Run-in period	Day after final IMP administration
Clinical laboratory value	Before IMP administration on Day 1	Day after final IMP administration
Vital signs	Before IMP administration on Day 1	Day after final IMP administration
12-lead ECG	Run-in period	Day after final IMP administration
Serum sodium concentration, serum potassium concentration, serum osmolality, biomarker	Before IMP administration on Day 1	-
Daily urinary output, daily fluid intake, daily water balance, daily sodium urinary excretion, daily potassium urinary excretion, urinary osmolality	During 24 hours before start of IMP administration on Day 1	-

^aWhen multiple data are collected during the run-in period, the data closest to Day 1 will be used as baseline.

4 Sample Size

The primary objective of this clinical trial is to compare tolvaptan exposure in order to investigate the dose of OPC-61815 injection required to achieve exposure equivalent to tolvaptan 15-mg tablet for use in conducting phase 3 confirmatory clinical trials of OPC-61815. The number of subjects required for this purpose was determined to be at least 10 subjects per group (50 subjects in total) who complete blood sampling for measurement of plasma drug concentrations up until 24 hours postdose on Day 1. In consideration of the possibility of some subjects withdrawing from the trial prior to 24 hours postdose on Day 1, the approximate target number of subjects for the start of IMP administration is set at 11 subjects per group (55 subjects in total).

5 Statistical Analysis Sets

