9.4 Vital Sign Data

Descriptive statistics will be calculated for vital signs together with the changes from baseline at each time point and after final administration.

9.5 **Electrocardiogram Data**

Descriptive statistics of each 12-lead electrocardiogram (ECG) parameter and the changes from baseline in each parameter at each time point and after final administration will be calculated.

The number and percentage of subjects who have a QTc interval (QTcB, QTcF) of “> 450 msec”, “> 480 msec”, and “> 500 msec” at at least one postdose time point or after final administration will be calculated. In addition, the number and percentage of subjects who show a change of “> 30 msec” and “> 60 msec” in QTc interval from baseline at at least one postdose time point or after final administration will be calculated. The numbers and percentages of subjects will also be calculated at baseline and each postdose time point in the same manner. “Normal” and “abnormal” assessments at each postdose time point and after final administration compared with baseline will be summarized in a shift table. “Normal” and “abnormal” assessments by the trial site (investigator or subinvestigator) will be used instead of the assessments by the central ECG analysis laboratory.

10 **Pharmacokinetic Analyses**

This section describes the pharmacokinetics of primary and secondary endpoints.

- 1) Endpoints
 - a) Primary Endpoint :
 - C_{max} and AUC_{24h} of plasma tolvaptan on Day 1 of treatment period
 - b) Secondary Endpoints:
 - i) Plasma concentrations of OPC-61815, tolvaptan, DM-4103 and DM-4107
 - ii) Plasma pharmacokinetic parameters of OPC-61815, tolvaptan, DM-4103 and DM-4107
 - Day 1 of treatment period: C_{max}^a , AUC_{24h}^a , AUC_t , AUC_{∞} , t_{max} , λ_z , $AUC_ \%Extrap$, t_{last} , $t_{1/2,z}$, CL^b , CL/BW^b , V_z^b , V_z/BW^b , CL/F^c , $CL/F/BW^c$
 - Day 1, Day 2, Day 3, Day 4, and Day 5 of treatment period: C_{24h}^d
 - Day 5 of treatment period: $R_{5,ac}(C_{24h})$

^aExcluding tolvaptan

^bCalculated only for OPC-61815 after administration of OPC-61815 injection

^cCalculated only for tolvaptan after administration of tolvaptan 15-mg tablet

^dFor calculation of descriptive statistics, C_{24h} will be handled as plasma concentrations.

iii) Ratio of the AUC of metabolite to that of OPC-61815^e

Day 1 of treatment period: AUC_{∞} , AUC_{24h} , and AUC_t

^eCalculated only for the OPC-61815 injection groups

2) Handling of Data

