- If the administration method specified in the protocol (see below) is not applied to administer the IMP, the instructions listed below will be followed.
 - a) Tolvaptan 15-mg tablet group: One tablet is taken with water once daily.
 - For the tolvaptan 15-mg tablet group, in the event of overdosing or missing a dose, plasma concentration at predose on that day will be used, but none of the plasma concentrations after that time point (including the plasma concentrations after administration on the following day or later) will be used for the calculation of descriptive statistics.

b) OPC-61815 injection 2 mg, 4 mg, 8 mg, and 16 mg groups: The assigned dose is administered intravenously for 1 hour (acceptable range: 55 to 65 minutes) once daily.

- For OPC-61815 injection 2 mg, 4 mg, 8 mg, and 16 mg groups, in the event of insufficient dose administration, overdosing, or missing a dose, plasma concentration at predose on that day will be used, but the plasma concentrations after that time point (including the plasma concentrations after administration on the following day or later) will not be used for the calculation of descriptive statistics. In the event of full dose administration but outside the acceptable window because of interruption, etc or full dose administration with an unknown administration time, plasma concentrations after administration on that day will not be used (plasma concentrations at predose on the following day and after administration on the following day or later will be used).

Of the parameters calculated with data including plasma concentrations excluded from descriptive statistics, the parameters determined to be unsuitable for the calculations will not be adopted.

- For each analyte, if a quantitative value is obtained at predose on Day 1, and the value exceeds 5 % or more of the highest value of the period between 1 hour and 24 hours after administration on Day 1, the plasma concentrations for that analyte at predose and thereafter will be excluded from the calculation of descriptive statistics. Parameters of the analyte with all of the plasma concentrations excluded from the calculation of descriptive statistics will not be adopted.
- b) Plasma concentrations below lower limit of quantitation that occur prior to and after the first measurable concentration will be imputed to 0 (ng/mL) and missing. Lower limit of quantitation of each analyte is listed in [Appendix 3](#).

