- c) Concentrations reported as Not Analyzed (NA) or Not Determined (ND) are regarded as missing values.

3) Statistical Analysis Method

- a) Primary Endpoint
 - i) For primary endpoint, analysis will be performed for the subject population set of the pharmacokinetic analysis set for which at least one primary endpoint was obtained.
 - ii) For “[1a\)](#) Primary Endpoint,” descriptive statistics will be calculated for each parameter by treatment group.
 - iii) For “[1a\)](#) Primary Endpoint,” logarithm converted value (natural logarithm) will be used to calculate the mean difference (each OPC-61815 injection group – tolvaptan 15-mg tablet group) and the 95% confidence interval of the difference.
- b) Secondary Endpoints
 - i) For secondary endpoints, analyses will be conducted for the pharmacokinetic analysis set.

- ii) For “1)b) Secondary Endpoints i),” descriptive statistics at each blood sampling point will be calculated by administration date, analyte, and treatment group.
- iii) For “1)b) Secondary Endpoints ii)” (excluding λ_z , λ_z (lower), λ_z (upper), λ_z (point) and λ_z (Rsq)), descriptive statistics of each parameter will be calculated by administration date, analyte, and treatment group.
- iv) For “1)b) Secondary Endpoints iii),” descriptive statistics of each parameter will be calculated by analyte and treatment group.

c) Descriptive Statistics

Descriptive statistics to be calculated for plasma drug concentration will be number of analyzed subjects, number of subjects for which concentrations data were obtained (excluding missing data or unadopted data), arithmetic mean, standard deviation, coefficient of variation, minimum, median, and maximum. However, descriptive statistics will be calculated only at the time point when the number of subjects for which data were obtained (excluding missing data or unadopted data) exceeds half of the number of analyzed subjects in each group.

For variables other than plasma drug concentration, descriptive statistics to be calculated will be number of analyzed subjects, number of subjects for which data were obtained (excluding incalculable data or unadopted data), arithmetic mean, standard deviation, coefficient of variation, geometric mean, minimum, median, and maximum. However, descriptive statistics will be calculated only when the number of subjects for which data were obtained (excluding Not Determined (ND) or unadopted data) exceeds half of the number of analyzed subjects in each group.

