PKT-1.1.1.3 Individual and Summary of DM-4103 Plasma Concentration Following Single Intravenous Administration of OPC-61815

PKT-1.1.1.4 Individual and Summary of DM-4107 Plasma Concentration Following Single Intravenous Administration of OPC-61815

PKT-1.1.2.1 Individual and Summary of OPC-61815 Plasma Pharmacokinetic Parameters Following Single Intravenous Administration of OPC-61815

PKT-1.1.2.2 Individual and Summary of OPC-41061 Plasma Pharmacokinetic Parameters Following Single Intravenous Administration of OPC-61815

- PKT-1.1.2.3 Individual and Summary of DM-4103 Plasma Pharmacokinetic Parameters Following Single Intravenous Administration of OPC-61815
- PKT-1.1.2.4 Individual and Summary of DM-4107 Plasma Pharmacokinetic Parameters Following Single Intravenous Administration of OPC-61815
- PKT-1.1.3.1 Individual and Summary of OPC-61815 Plasma Concentration Following Multiple Intravenous Administration of OPC-61815
- PKT-1.1.3.2 Individual and Summary of OPC-41061 Plasma Concentration Following Multiple Intravenous Administration of OPC-61815
- PKT-1.1.3.3 Individual and Summary of DM-4103 Plasma Concentration Following Multiple Intravenous Administration of OPC-61815
- PKT-1.1.3.4 Individual and Summary of DM-4107 Plasma Concentration Following Multiple Intravenous Administration of OPC-61815
- PKT-1.1.4.1 Individual and Summary of OPC-61815 Plasma Trough Concentration Following Intravenous Administration of OPC-61815
- PKT-1.1.4.2 Individual and Summary of OPC-41061 Plasma Trough Concentration Following Intravenous Administration of OPC-61815
- PKT-1.1.4.3 Individual and Summary of DM-4103 Plasma Trough Concentration Following Intravenous Administration of OPC-61815
- PKT-1.1.4.4 Individual and Summary of DM-4107 Plasma Trough Concentration Following Intravenous Administration of OPC-61815
- PKT-1.1.6.1 Individual and Summary of OPC-61815 Plasma Accumulation Parameters Following Multiple Intravenous Administration of OPC-61815
- PKT-1.1.6.2 Individual and Summary of OPC-41061 Plasma Accumulation Parameters Following Multiple Intravenous Administration of OPC-61815
- PKT-1.1.6.3 Individual and Summary of DM-4103 Plasma Accumulation Parameters Following Multiple Intravenous Administration of OPC-61815
- PKT-1.1.6.4 Individual and Summary of DM-4107 Plasma Accumulation Parameters Following Multiple Intravenous Administration of OPC-61815

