- PKF-1.1.6.1 Mean OPC-61815 Plasma Trough Concentrations Following Intravenous Administration of OPC-61815
- PKF-1.1.6.2 Mean OPC-41061 Plasma Trough Concentrations Following Intravenous Administration of OPC-61815
- PKF-1.1.6.3 Mean DM-4103 Plasma Trough Concentrations Following Intravenous Administration of OPC-61815
- PKF-1.1.6.4 Mean DM-4107 Plasma Trough Concentrations Following Intravenous Administration of OPC-61815
- PKF-1.1.7.1 Median OPC-61815 Plasma Trough Concentrations Following Intravenous Administration of OPC-61815
- PKF-1.1.7.2 Median OPC-41061 Plasma Trough Concentrations Following Intravenous Administration of OPC-61815
- PKF-1.1.7.3 Median DM-4103 Plasma Trough Concentrations Following Intravenous Administration of OPC-61815

- PKF-1.1.7.4 Median DM-4107 Plasma Trough Concentrations Following Intravenous Administration of OPC-61815
- PKF-1.1.8.1 Mean OPC-61815 Plasma Concentrations Following Single and Multiple Intravenous Administration of OPC-61815
- PKF-1.1.8.2 Mean OPC-41061 Plasma Concentrations Following Single and Multiple Intravenous Administration of OPC-61815
- PKF-1.1.8.3 Mean DM-4103 Plasma Concentrations Following Single and Multiple Intravenous Administration of OPC-61815
- PKF-1.1.8.4 Mean DM-4107 Plasma Concentrations Following Single and Multiple Intravenous Administration of OPC-61815
- PKF-1.1.9.1 Median OPC-61815 Plasma Concentrations Following Single and Multiple Intravenous Administration of OPC-61815
- PKF-1.1.9.2 Median OPC-41061 Plasma Concentrations Following Single and Multiple Intravenous Administration of OPC-61815
- PKF-1.1.9.3 Median DM-4103 Plasma Concentrations Following Single and Multiple Intravenous Administration of OPC-61815
- PKF-1.1.9.4 Median DM-4107 Plasma Concentrations Following Single and Multiple Intravenous Administration of OPC-61815
- PKF-1.1.10.1 OPC-61815 Plasma Concentrations Following Multiple Intravenous Administration of OPC-61815
- PKF-1.1.10.2 OPC-41061 Plasma Concentrations Following Multiple Intravenous Administration of OPC-61815
- PKF-1.1.10.3 DM-4103 Plasma Concentrations Following Multiple Intravenous Administration of OPC-61815
- PKF-1.1.10.4 DM-4107 Plasma Concentrations Following Multiple Intravenous Administration of OPC-61815
- PKF-1.1.11.1 OPC-61815 Plasma Trough Concentrations Following Intravenous Administration of OPC-61815
- PKF-1.1.11.2 OPC-41061 Plasma Trough Concentrations Following Intravenous Administration of OPC-61815

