Appendix 3**Molecular Weight and Quantitation Limit of Plasma Drug Concentration**

Analyte	Molecular Weight ^{a)}	Lower Limit of Quantitation (ng/mL) ^{b)}
OPC-61815	572.88 (sodium salt)	Not Appreciable
	528.92 (free base)	2.00
OPC-41061	448.94	2.00
DM-4103	478.92	2.00
DM-4107	480.94	2.00

a): Molecular Weight Information, Issued on 1 Apr 2016

b): Study Protocol (Study No. P17-21515, Issued on 9 Feb 2018)

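### Tolvaptan C24h values below 2.00 ng/mL are dropped as missing, so a trough mean or minimum (and, ties aside, median) printed with some subjects below the limit is too high

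*SAP*

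**What the plan says.** - **SAP 10 2) b)**: concentrations below the limit that "occur prior to and after the first measurable concentration will be imputed to 0 (ng/mL) and missing". The only workable reading is paired: before the first measurable value, 0; after it, missing.
- **SAP 10 1) b), footnote d**: for descriptive statistics, C24h "will be handled as plasma concentrations". It is a secondary endpoint on Days 1 to 5.
- **SAP 10 3) c)**: for concentrations, "descriptive statistics will be calculated only at the time point when the number of subjects for which data were obtained" exceeds half of those analyzed in the group. Missing and unadopted values do not count as obtained. The table shows the number analyzed, the number with data, mean, SD, CV, minimum, median and maximum. It does not show the number below the limit.
- **SAP Appendix 3**: the tolvaptan (OPC-41061) limit is 2.00 ng/mL.
- **SAP Appendix 1**: the planned outputs include PKT-1.1.4.2, "Individual and Summary of OPC-41061 Plasma Trough Concentration Following Intravenous Administration of OPC-61815", and PKF-1.1.6.2, "Mean OPC-41061 Plasma Trough Concentrations Following Intravenous Administration of OPC-61815", with matching median figures and tablet-arm versions.
- **SAP 4**: at least 10 subjects per group with complete Day 1 sampling, and about 11 per group starting treatment.
- **Protocol 3.7.5.1.1 (3)**: the single 24-hour sample after each later dose "is selected to confirm steady-state has been reached".

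**The concern.** A trough below the limit that follows measurable Day 1 values is not unknown. It lies between 0 and 2.00 ng/mL. Making it missing treats that subject as if the level could have been anywhere, and every value removed this way comes from the bottom of the distribution. No other rule in the SAP puts the information back.

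C24h is the only drug level sampled after Day 1, so the trough tables and figures are the trial's whole picture of exposure on repeated dosing. Someone reading the summary rows sees a gap between the number analyzed and the number with data. They cannot tell whether the gap is measured-and-low results or samples that were not analyzed, not determined or not adopted.

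**Working it through.** The plan states no figure on this point, so there is none to reproduce.

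**1. Direction, without a model.** Let n be the number analyzed and k the number below the limit. Statistics are printed when n - k > n/2, so k can reach 4 of 10 or 5 of 11.

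- Mean: printed minus true = (k/n) x (mean of kept values - mean of dropped values). Kept values are at least 2.00 and dropped values are below it, so this is always positive.
- Minimum: the printed value is the (k+1)th smallest and can never fall below 2.00.
- Median, 4 of 10 below: ranks 5 to 10 remain, so the average of the 7th and 8th is printed. The true median is the average of the 5th and 6th, and both were measured.
- Median, 5 of 11 below: ranks 6 to 11 remain, so the average of the 8th and 9th is printed. The true median is the 6th, which was measured.

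**2. Hand example (invented values, ng/mL).** 0.6, 1.0, 1.4, 1.8, 2.3, 2.9, 3.6, 4.5, 6.0, 9.0; four are below 2.00.

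- True mean 33.1/10 = 3.31; true median (2.3 + 2.9)/2 = 2.60; true minimum 0.6.
- Printed mean 28.3/6 = 4.72 (+42%); printed median (3.6 + 4.5)/2 = 4.05 (+56%); printed minimum 2.3.
- With the four kept at 0 or at 2.00, the mean is 2.83 or 3.63, which brackets the truth. The median is 2.60 either way.

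**3. Illustrative size.** Inputs:

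- Cmax 109.6 ± 22.07 ng/mL for 8 mg over 1 hour, tmax 1.5 h (Protocol Table 2.3-5, a simulation from healthy-adult data). It is scaled by dose/8, with CV 22.07/109.6 = 20%.
- Half-life lognormal, CV 30% (assumed). Healthy-adult group means are 2.2 to 5.7 h (Protocol 1.2 (1)). Slower hepatic metabolism is expected in heart failure (Protocol 2.3 (1)), but no half-life is given.
- C24h = Cmax x 2^(-22.5/half-life).

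The three settings below were chosen because the arm sits near the limit: 4 mg at 5.7 h, 2 mg at 7 h and 8 mg at 4 h. Inflation is the average printed value over the average true value in the same arms.

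| Below limit | Mean | Median |
|---|---|---|
| 1 of 10 | 1.08-1.09 | 1.06-1.08 |
| 2 of 10 | 1.16-1.20 | 1.15-1.20 |
| 3 of 10 | 1.27-1.33 | 1.25-1.35 |
| 4 of 10 | 1.39-1.50 | 1.43-1.60 |
| 5 of 11 | 1.47-1.61 | 1.57-1.81 |

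These take the stated half-life as the median of its distribution. Taking it as the mean leaves the mean column almost unchanged and gives medians of 1.41-1.57 at 4 of 10.

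**4. How often.** Percentage of 10-subject arms that print a C24h summary with at least one subject below the limit (2/4/8/16 mg):

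| Half-life | Taken as median | Taken as mean |
|---|---|---|
| 2.8 h | 0/0/0/3 | 0/0/0/1 |
| 4 h | 0/4/44/85 | 0/2/30/79 |
| 5.7 h | 22/85/67/30 | 13/79/75/39 |
| 7 h | 81/64/23/6 | 71/73/30/9 |
| 8 h | 84/34/8/2 | 87/43/12/3 |

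**5. Which half-life fits the Cmax used.** With a linear rise to 1.5 h and then a mono-exponential fall, AUC24h = 0.5 x 1.5 x 109.6 + 109.6 x (h/ln 2) x (1 - 2^(-22.5/h)). At h = 2.8 this is 82 + 441 = 523, against 521.1 in Table 2.3-5. At 4 h it is 702 and at 5.7 h it is 925. So 2.8 h fits both simulated values. There the typical C24h is 0.10, 0.21, 0.42 and 0.84 ng/mL for 2 to 16 mg, and nearly every arm prints nothing.

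**The case against.** The strongest reply is that nothing is decided on these outputs. C24h is secondary, no between-arm comparison of it is planned, and its stated use is to confirm steady state. The bias is the same on each day on average if the drug does not accumulate, and Protocol 3.2.1 says it does not. The more-than-half rule suppresses the worst cases, the number with data is printed, and the tables list individual values beside the summary. The sizes above come from arms picked for being near the limit. In absolute terms, 4 of 10 below raises the mean by only about 1.1 to 1.8 ng/mL, against mean Cmax of 27 to 110 ng/mL in those arms. All of this stands, and it limits the harm. It does not make a printed summary correct, and the number below the limit is still not shown.

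The documents do not support three stronger readings that a reader might infer:

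- *The primary comparison is biased.* Cmax is the highest measured value and is untouched. The effect on AUC24h depends on the sponsor's noncompartmental manual, which is not among the documents, so no bias can be claimed.
- *The rule would hide accumulation.* That needs real accumulation. With r = 2^(-24/h), linear superposition gives a fifth-to-first-dose C24h ratio of (1 - r^5)/(1 - r): 1.02 at 4 h, 1.06 at 5.7 h, 1.10 at 7 h and 1.23 at 10 h. By 10 h few arms above 2 mg have anyone below the limit.
- *Most trials would be affected.* The frequency moves from near zero to over 80% of arms within the half-lives tried, and it shifts with how the half-life is centred.

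**Conclusion.** The concern holds on the text, as a minor point. The direction rests on ordering alone: with 1 to 4 of 10, or 1 to 5 of 11, below 2.00 ng/mL, the printed mean and minimum are too high, and so is the median unless values tie. The sizes in the working are conditional on an arm being near the limit. They assume dose-proportional Cmax from a healthy-adult simulation, a mono-exponential fall and a half-life CV of 30%. How often it happens cannot be settled from the documents: rarely near 2.8 h, commonly in at least one injection arm at about 4 to 8 h. The consequence is confined to the descriptive trough tables and figures.

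**What to change.** **SAP 10 2) b)**: keep the omission of post-peak below-limit values for the noncompartmental calculation only. State that in summaries of concentrations and C24h they count as below-limit results, not as missing.

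**SAP 10 3) c)**, for concentrations and C24h:

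- Report the number below the limit by arm and day, separately from NA, ND and unadopted data.
- Compute the median with below-limit values ranked lowest. When exactly half are below, show the two middle values (<2.00 and the lowest measured one). When more than half are below, show <2.00.
- Print the minimum as <2.00 whenever any value is below the limit.
- Keep the more-than-half rule for mean, SD and CV. Where a mean is printed with some values below the limit, footnote how many. Then either give the mean with those values at 0 and at 2.00 as bounds, or use one substitution stated in advance.
- Use the same values in the mean and median trough figures.

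Cost: SAP wording and some reprogramming of the concentration and trough outputs. No new data are needed, and Cmax and the noncompartmental calculation do not change. Any single substitution for the mean is one convention among several and slightly distorts SD and CV. The count, median and minimum rules do not depend on that choice.
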